### 3. Study Design

Prospective cohort study (observational). We will use the established HDSS to set up population-based COVID-19 surveillance in a household cohort. From any individual in this population reporting any respiratory sign (symptom or lowered peripheral oxygen saturation) or loss of smell or taste, with or without fever, we will collect a respiratory specimen and test these for SARS-CoV-2 virus by PCR, during 12 months. These cases will be identified through bi-weekly household visits, through an alert system involving community leaders and HDSS interviewers, or when presenting with symptoms at healthcare centres or at the referral hospital. Identified healthcare facilities will then alert the study team if a possible case from the HDSS population is consulted or admitted, if the patient agrees. Demographic, epidemiological and clinical data (comorbidities, medication, obesity, HIV, TB, smoking) of possible cases and of the source population will be recorded at baseline; recent illness, potential risk exposure of each household member (including duration and type) to SARS-CoV-2 positive individuals, uptake of measures to reduce exposure/transmission, and barriers to the uptake of such measures, will be

recorded/updated during every household visit. COVID-19 vaccination status will be recorded from possible cases and compared to that of a subset of the population, in a case-cohort design to determine vaccine effectiveness against symptomatic COVID-19.

An age-stratified serial sero-survey will be conducted at baseline in a subset of the population in the population-based COVID-19 surveillance, and at 3, 6 and 12 months, after confirmation of community transmission. Recording vaccination status of all sero-survey participants, we will determine vaccine effectiveness against SARS-CoV-2 seroconversion in a cohort design.

Household transmission will be specifically investigated, by investigating contact history, vaccination status, and the presence of SARS-CoV-2 virus and serology among household members twice during the month after the symptom onset of a household index case.

## 4. Participants, Population & Selection

### 4.1 Setting

Polana Caniço, peri-urban Maputo, Mozambique: a health- and demographic surveillance system (HDSS) covering a population of 15,393, in the catchment area of the Polana Caniço General Hospital (PCGH), one out of two COVID-19 referral facilities in Maputo.

The population in peri-urban Polana Caniço is relatively representative of the increasingly urban population in Southern Africa, having young and mobile inhabitants. Moreover, the population suffers increasingly from non-communicable diseases, and prevalence of HIV and active tuberculosis is presumed to be important. Research gaps on COVID-19 transmission dynamics include whether the reproduction number could be different in such different (eg. younger) population. Also, the potential association between (uncontrolled) HIV infection or (active) tuberculosis and COVID-19 infection and severe disease, needs to be elucidated.

The Polana Caniço-HDSS has been established since 2017. In total, as of time of writing, 2108 households (defined as residents of the same building, sharing a cooking area) have been enrolled in the HDSS. All members residing in the household for at least 3 months (infants, children, adults, elderly) are enrolled in the HDSS. Surveillance rounds are currently carried out six-monthly. Demographic and health indicators collected in each surveillance round include but are not limited to: fertility/birth rate, mortality/cause of death, migration, disease cases, trauma and violence, socioeconomic status, water and sanitation facilities, risk factors for the acquisition of chronic diseases, women's health and family planning, immunization, risk behaviours and cultural practices related to the transmission of STI (including HIV and syphilis). Testing for HIV and syphilis is planned to be added as part of the surveillance rounds, from October 2020 onwards. Data on births, deaths, internal and external migration, pregnancies and their outcomes, and any other relevant events from a demographic perspective, are continuously reported by community key informants and confirmed through home visits.

### 4.2 Selection and recruitment

All households in the HDSS (2108 during the last round in 2019) consenting to participate in the study will be **visited biweekly** by a trained HDSS interviewer, following the same procedures as in routine HDSS rounds, specified in the HDSS protocol (Instituto Nacional de Saude, 2016). We assume the same number of households will consent to participate as in other HDSS rounds. Based on previous experience with the HDSS, we expect the HDSS interviewer to visit 6 households per working day on average.

Household heads, or an adult delegated by the household head, will be asked about COVID-19 consistent symptoms among any consented household member, using a structured questionnaire. If a household member is identified by the household head as reporting any respiratory sign (symptom or lowered peripheral oxygen saturation) or loss of smell or taste, with or without fever, in the last week, i.e. a possible COVID-19 case, this household member will be asked to consent for participating, to respond to a structured questionnaire and to collect a nasal swab sample for SARS-CoV-2 testing. Specimens will be tested for SARS-CoV-2, using RT-PCR (at INS in Marracuene). Possible COVID-19 cases in the HDSS households will be detected through four entry points:

- Biweekly HH visits
- Phone call by patient (when symptoms occur)
- Phone call by study team (as currently done in HDSS)
- HDSS household members presenting as COVID-19 suspected case in healthcare facility

If meeting the COVID-19 admission criteria as per national guidance, the possible COVID-19 case will be referred to the Polana Caniço General Hospital (PCGH), the closest healthcare facility and COVID-19 patient management centre.

An **age-stratified random sample** of that population will be selected for the **repeated sero- and social mixing survey**. By age stratum (0-17 years; 18-50 years; >50 years) we randomly select 800 individuals (simple random sample per age stratum; 2400 in total) from the Polana Caniço HDSS population (regardless of infection or disease status or history), from whom during home visits dried blood spots will repeatedly be collected at 0, 3, 6 and 12 months, vaccination status against COVID-19 will be recorded, and who will be asked to respond to a social mixing questionnaire. A HDSS sampling frame of all individual participants in the HDSS with socio-demographic data and unique identifiers, is available, and will be used to select a simple random sample of individuals by age group.

When a member of a household with no prior widespread transmission (see exclusion criteria) tests SARS-CoV-2 positive, we will revisit the household twice for a household transmission investigation: as soon as possible after the result of the household index case (baseline), and once again one month after symptom onset of the household index case. An initial contact report form will be filled in as soon as possible, ideally within 24 hours, after laboratory confirmation of the primary case in the household. Respiratory and dried blood spot samples will be collected of everyone considered resident (as defined by the HDSS) in the household and who has been in contact with the SARS-CoV-2 positive individual, regardless of age and presence or absence of symptoms. Respiratory samples will be analysed by RT-PCR for SARS-CoV-2 to assess presence of virus and viral load. The dried blood spots for serology on the Luminex assay. Data will be collected on household exposures of contacts and vaccine receipt. Symptomatic household contacts will be tested whenever symptoms appear, as part of the population-based surveillance. This is planned for upto 100 household index cases.

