All HDSS households will be visited by a trained HDSS interviewer to present the study and ask for informed consent (i) by the household head for the population-based surveillance and (ii) by the individuals selected for the age-stratified serial sero-survey. During this same visit, if the household head consented, the demographics data (baseline household visit form) will be verified and updated. A study household card with unique IDs of each household member will be provided (code containing the housing block, household id and sequential household member number). Household members will be sensitized on symptoms related to COVID-19, are asked to keep track of possible symptoms they may develop, and inform the study team by phone if a household member has a respiratory symptom, loss of smell or taste, so that upon assessment he/she can be asked to be swabbed for virological testing. In case a household member presents with symptoms which classify him/her as a possible case, a separate individual informed consent procedure for nasal swabbing will have to be performed prior to sampling. This ICF covers sampling for the first episode and any subsequent episode during the study period when nasal sampling would be indicated. Also during the baseline household visit, if full informed consent was provided (both for surveillance by the household head and for the sero- and social mixing survey by the individual household member), individual household members selected for the sero-survey will be asked for a baseline dried blood spot sample on filter paper, by administering a few blood drops through a finger prick.

Every two weeks a trained interviewer from the HDSS team will do calls to the head of the household or his representative, where during the call he will fill out a questionnaire (Household follow-up visit form) recording any respiratory symptoms, fever or other indicative sign of COVID-19 (at the time of the phone call, or in the last two weeks, if these symptoms go away), vaccination against COVID-19, and medical appointments that any family member has had.

Meanwhile (if applicable), demographic changes or changes in the chronic medical conditions of family members will be recorded. If a family member reports a respiratory sign or loss of smell or taste, with or without fever (possible case), a trained interviewer will do a home visit to this household.

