Household transmission investigation	100 household primary cases and their household members (who have been in contact with the index case	· baseline household transmission form

Table 5 . Samples collected during each surveillance and sero-survey study visit

Study visit	Baseline (M0)	Biweekly visit	M3	Biweekly visit	M6	Biweekly visit	M9	Biweekly visit	M12	possible case visit	case follow-up visit (D28)	case follow-up visit (D56)
Tests to carry out	NASAL SWAB											
RT-PCR to detect SARS-CoV-2 viral RNA	*	*	*	*	*	*	*	*	*	*	X	
DRIED BLOOD SPOT (DBS)												
Luminex (anti-SARS-CoV-2 serology)	X		X		X					X		
Approx. volume of collected blood	450ul		450ul		450ul					450ul		

\* A nasal swab will only be collected if an individual is identified as a possible COVID19 case (respiratory symptoms, loss of smell or taste, with or without fever). All tests will be carried out at the INS-Marracuene lab in Maputo, Mozambique.

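### Sections 4.2 and 5.1 give different symptom look-backs for a possible case (one week against two) and nothing says which governs; if the one-week rule is applied at two-weekly contacts, the primary symptomatic incidence rate is biased low.

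*Combined protocol and SAP*

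**What the plan says.** Section 4.2 has households contacted biweekly. A member is eligible for the possible-case questionnaire and nasal swab if the household head reports a respiratory sign "or loss of smell or taste, with or without fever, in the last week, i.e. a possible COVID-19 case".

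Section 5.1 describes the same routine contact differently. "Every two weeks a trained interviewer from the HDSS team will do calls", and the form records symptoms present "at the time of the phone call, or in the last two weeks, if these symptoms go away". The next step carries no window of its own: "If a family member reports a respiratory sign or loss of smell or taste, with or without fever (possible case"), an interviewer goes to the home. Table 2 confirms that the interval is 14 days, since each row stands for two weeks.

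The synopsis, Table 1 and Section 3 state who is swabbed without any look-back. So does the footnote to Table 5, which makes the definition decisive for surveillance and sero-survey visits: "A nasal swab will only be collected if an individual is identified as a possible COVID19 case".

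There are other ways in. Section 4.2 lists "Phone call by patient (when symptoms occur"), "Phone call by study team (as currently done in HDSS") and presentation at a health facility. Section 3 adds detection "through an alert system involving community leaders and HDSS interviewers".

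Table 1 marks symptomatic infections per person-month as a primary outcome. For this rate, Section 7.1 plans a correction for RT-PCR sensitivity according to the delay from onset to test.

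**The concern.** With contacts 14 days apart, a 7-day look-back leaves the first half of each interval uncovered for illnesses that have already ended. Such a person is not a possible case under 4.2 and is not swabbed, so cannot become a confirmed case. Their person-time still enters the denominator, so any error is downward.

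Nothing later in the plan repairs this. The adjustment in 7.1 applies to swabs that were taken and says nothing about episodes never tested. The switch to testing every tenth possible case, once confirmed cases exceed 50 per week, samples from the same restricted list. Section 7.1 also scales the clinical rate up to an infection incidence rate, so a shortfall could carry forward. The other primary outcome marked in Table 1, the annual infection attack rate, comes from the sero-survey and does not depend on who is swabbed.

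If the two sections are read together, so that the form records two weeks but the swab is limited to the last week, the early episodes are on record but untested, and 7.1 plans no analysis for them.

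**Working it through.** **The plan's own figure (Section 7.2).** Inputs: population 15,393, annual attack rate 40%, symptomatic share 50%, share identified by surveillance 90%.

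- Cases: 15,393 × 0.40 × 0.50 × 0.90 = 2,771. The plan states 2,790, which corresponds to a population of 15,500; the difference is 0.7%.
- Rate: 0.40 × 0.50 × 0.90 / 12 = 0.0150, or 1.50 per 100 person-months, as stated. The exact Poisson 95% interval is 1.44 to 1.56 (stated 1.45 to 1.56).

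**What a 7-day look-back misses at 14-day contacts.** The documents give neither illness duration nor the yield of the other routes, so three assumptions are needed:

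- onset is uniform over the 14 days before the contact;
- every episode lasts D days;
- other routes catch a share r of what the scheduled contact misses.

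An episode that began u days before the contact ended u − D days before it. It falls outside the window if u − D > 7, that is, if u lies between 7 + D and 14. Hence

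missed share = (1 − r) × max(0, (7 − D)/14).

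| D (days) | r = 0 | r = 50% | r = 80% |
|---|---|---|---|
| 1 | 43% | 21% | 9% |
| 3 | 29% | 14% | 6% |
| 5 | 14% | 7% | 3% |
| 7 or more | 0% | 0% | 0% |

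For D = 3: (7 − 3)/14 = 0.286; × 0.5 = 0.143; × 0.2 = 0.057.

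With a 14-day look-back the missed share is zero for every D.

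**On the scale of the primary outcome.** This takes 1.50 as the rate that full coverage of the interval would give, which is a further assumption.

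- All episodes last three days: 1.50 × (1 − 0.286) = 1.07 at r = 0, 1.29 at r = 50%, 1.41 at r = 80%.
- A quarter last three days and the rest 7 days or more: the loss at r = 0 is 0.25 × 4/14 = 7.1%, giving 1.39. At r = 50% and 80% the rate is 1.45 and 1.48.

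In the second case the r = 0 value lies below the planned interval of 1.45 to 1.56, the r = 50% value is at its lower limit, and the r = 80% value is inside it. These are illustrations, not estimates.

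**The case against.** The strongest reply is that most of the text points to no gap. The one-week phrase occurs once. Section 5.1, the procedures section, covers the whole interval, includes resolved symptoms, calls a reported sign a possible case and sends a visit. The other statements of the rule set no time limit. The household follow-up form, which fixes the question actually asked, is not in the documents. All of this stands, so the bias is a possibility and has not been shown. It does not remove the contradiction, because 4.2 is an explicit definition and no passage subordinates it to 5.1.

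A second reply is that the loss needs several things at once: the 4.2 rule is the one used, every qualifying sign has gone, it went more than 7 days before the contact, and no other route caught it. Households are told which symptoms to watch for and asked to phone (5.1), an interviewer can be sent between visits (5.1), and airtime for such calls can be reimbursed (10.6). Contacts in up to 100 households are swabbed whether or not they have symptoms (4.2). This also stands. It shrinks the loss by an unknown amount and is why r appears in the formula.

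A third reply is that 7.2 already allows for 10% of cases not being identified. That figure is a planning assumption tied to neither window, and 7.1 does not use it to correct the rate.

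A reader might infer that the study will miss about 43% of symptomatic cases. The documents do not support this. That figure needs every illness to last one day and every other route to fail.

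**Conclusion.** The point holds as an internal contradiction of minor to moderate weight. Sections 4.2 and 5.1 define the swab-triggering window differently and nothing in the documents resolves it. If 4.2 is applied, the primary symptomatic incidence rate is biased low for short illnesses early in the interval that no other route catches, and 7.1 cannot recover them. If 5.1 is applied, this bias does not arise.

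The size is not estimable from the documents. Under uniform onset and fixed duration it runs from zero, for illnesses of 7 days or more, to 6% for three-day illnesses with 80% caught elsewhere and 29% with none caught elsewhere.

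Two stronger readings should be resisted. One is that the plan deliberately chose a one-week window as a design feature; a single phrase at odds with the procedures section does not show that. The other is that the primary rate is known to be biased; that depends on which window the interviewers use, which cannot be seen here.

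**What to change.** Reconcile 4.2, 5.1 and the household follow-up questionnaire to one look-back that covers the whole interval since the last contact (nominally two weeks, as 5.1 already has), and state that this window decides who is a possible case for swabbing. Keep the adjustment in 7.1 by delay from onset to test.

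The change is one line in 4.2 and a check of the form. The price, compared with a one-week rule, is somewhat more swabs and later ones with lower PCR yield. Under the same assumptions and scheduled contact only, for three-day illnesses:

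- mean delay from onset to contact rises from (7 + 3)/2 = 5 days to 14/2 = 7 days;
- maximum delay rises from 10 to 14 days;
- swabs rise by up to 14/(7 + 3) = 1.40 times.

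The planned delay adjustment is meant for such later swabs, but the documents give no sensitivity values by delay. They also do not say which window the expected 8,000 swabs in Table 2 assume, so that number should be checked against the window adopted.

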### 4.3 Inclusion and exclusion criteria

In order to be eligible, study participants **must meet the following criteria**:

- » Any individual enrolled in the Polana Caniço-HDSS: all members residing in the household for at least 3 months (infants, children, adults, elderly), regardless of age, underlying conditions, medical history, infection or disease status or history;
- » Able and willing to provide written informed consent: by the household head for the surveillance; by each selected participant for the sero-survey and household investigations.
- » For household investigations, over 50% of the eligible household members and index case should have provided consent for anyone in the household to enrol.

Excluded from the household investigations: members of households in which more than 3 household members (including the index case) are known to have tested positive for SARS-CoV-2 in the past 7 days.

#### 4.4 Sample size

See table 1, above, and justification for the sample size calculation in section 7.4 Sample size and power.

#### 4.5 Withdrawal and termination of the study

##### ***Reasons for Withdrawal***

Participants may be withdrawn from the study if the participant or legally acceptable representative withdraws the consent. For participants who consented to participate, but who moved out of the study area during the study period, the months when residing in the study area will still be considered.

##### ***Handling of Withdrawals***

When the investigator has no news of the participant, he/she must make every effort to contact him/her, to establish the reason for the discontinuation. If all these attempts to contact the participant fail, the investigator can then declare the participant "lost to follow-up". The investigator should document all these attempts in the corresponding medical file.

##### ***Termination of Study***

If the study is prematurely terminated or suspended, the Sponsor will promptly inform the investigators/institutions, and the regulatory authority(ies) of the termination or suspension and the reason(s) for the termination or suspension. The EC's will also be informed promptly and provided the reason(s) for the termination or suspension by the Sponsor or by the investigator/institution, as specified by the applicable regulatory requirement(s).

### 5. Study Procedures

#### 5.1 Study/visit schedule

Table 2. Schedule of assessments for population-based surveillance. One row corresponds to two weeks.

we ek	month	Informed consent (1)	Sero- survey	Household visit (2)	Unscheduled visit for swab collection	Case Follow- up outcome (3)	Social mixing & uptake (4)
1	Oct20	x	x	x		x	
3				x	x	x	
5	nov/20			x	x	x	x
7				x	x	x	
9				x	x	x	

11	dec/20			x	x	x	
13			x	x	x	x	
15	jan/21			x	x	x	
17				x	x	x	x
19	feb/21			x	x	x	
21				x	x	x	
23	mar21			x	x	x	
25			x	x	x	x	x
27	apr/21			x	x	x	
29				x	x	x	
31	may21			x	x	x	
33				x	x	x	
35				x	x	x	
37	jun/21			x	x	x	
39				x	x	x	
41	jul/21			x	x	x	
43				x	x	x	
45	aug/21			x	x	x	
47				x	x	x	
49	sep/21			x	x	x	x
51			x	x	x	x	
53						x	
55						x	
TOTAL forms filled*		2800 for household surveillance,2400 for sero-survey,8000 for swab collection	2400*4= 9600	2800*5= 70000	8000	8000	2400*4= 9600
TOTAL samples*			2400*4= 9600		8000		

Type of sample		DBS for serology, collected at home**		nasal swab for PCR, collected at home**		
----------------	--	---------------------------------------	--	---	--	--

DBS = dried blood spot

1 Informed consent for household surveillance (by the household head) and sero-survey (by the selected individual or their caretaker) during baseline visit

2 During baseline visit adapted questionnaire to update population characteristics

3 Only of COVID-19 confirmed cases identified by the surveillance, at 28 and 56 days after symptom onset

4 We plan the social mixing survey rounds each time one month after the sero-survey, to spread the workload. The same participants from the sero-survey are asked to complete the questionnaire

\* estimated, based on the available information at the start of the study; we anticipate 8000 respiratory episodes (possible cases), based on previous data from the HDSS, adjusted for increased frequency of reporting (previous data was recorded during three-monthly rounds)

\*\* both serology testing of DBS and PCR testing of nasal swabs will be carried out at INS Marracuene. DBS samples are collected during pre planned visits, PCR samples when a possible case is identified. Nasal swabs undergo PCR testing the day following sample collection and results are communicated back to the individual (or his/her caretaker) that same day.

All HDSS households will be visited by a trained HDSS interviewer to present the study and ask for informed consent (i) by the household head for the population-based surveillance and (ii) by the individuals selected for the age-stratified serial sero-survey. During this same visit, if the household head consented, the demographics data (baseline household visit form) will be verified and updated. A study household card with unique IDs of each household member will be provided (code containing the housing block, household id and sequential household member number). Household members will be sensitized on symptoms related to COVID-19, are asked to keep track of possible symptoms they may develop, and inform the study team by phone if a household member has a respiratory symptom, loss of smell or taste, so that upon assessment he/she can be asked to be swabbed for virological testing. In case a household member presents with symptoms which classify him/her as a possible case, a separate individual informed consent procedure for nasal swabbing will have to be performed prior to sampling. This ICF covers sampling for the first episode and any subsequent episode during the study period when nasal sampling would be indicated. Also during the baseline household visit, if full informed consent was provided (both for surveillance by the household head and for the sero- and social mixing survey by the individual household member), individual household members selected for the sero-survey will be asked for a baseline dried blood spot sample on filter paper, by administering a few blood drops through a finger prick.

Every two weeks a trained interviewer from the HDSS team will do calls to the head of the household or his representative, where during the call he will fill out a questionnaire (Household follow-up visit form) recording any respiratory symptoms, fever or other indicative sign of COVID-19 (at the time of the phone call, or in the last two weeks, if these symptoms go away), vaccination against COVID-19, and medical appointments that any family member has had.

Meanwhile (if applicable), demographic changes or changes in the chronic medical conditions of family members will be recorded. If a family member reports a respiratory sign or loss of smell or taste, with or without fever (possible case), a trained interviewer will do a home visit to this household.

In case that the head of the household or his representative is not available by phone (number disconnected or unreachable or without contact details), an interviewer will perform a visit for this

household. In addition to calls, home visits to households will be performed every three months to collect data in person.

Any adolescent or adult able to self-administer a nasal swab will be asked to do so, at the participants home. For children or adults not capable of self-swabbing, the trained interviewer will put on personal protective equipment and collect a nasal swab. Preferentially, if confidentiality allows, the swab will be taken outside. Alternatively in a room without other household members. A 'Possible case report form', based on the WHO case report form, will be completed, recording symptoms, recent risk exposure, and potential contact with COVID-19 cases.

If in between household visits, a household member can inform the study team by phone when he/she develops any sign that could be indicative of COVID-19, so that a trained interviewer will be dispatched to assess whether the signs qualify for a possible case, complete the 'Possible case report form', and collect a nasal swab (again by self-swabbing if possible) at the possible cases' home.

If during household visits or through phone call, the interviewer is notified that a participating household member has been admitted to a healthcare facility or presented to the COVID-19 clinical management centre at Polana Caniço General Hospital, the participant will be actively approached, and if applicable, a 'Possible case report form' filled. If SARS-CoV-2 PCR testing has been done already, results will be requested and entered in a 'Possible case lab request and result form'. If no SARS-CoV-2 PCR testing has been done yet, a nasal swab will be collected if indicated, following the same procedure as above.

Household investigations will be held , whenever a household index case ) is identified, excluding households in which more than 3 household members (including the index case) are known to have tested positive for SARS-CoV-2 in the past 7 days. During household transmission investigation visits, all eligible household members will be proposed to self-administer a nasal swab if adolescent or adult, or a nasal swab will be collected by the interviewer if the participant is a child or unable to administer a nasal swab. A Dried blood spot sample will be collected. The household head will be requested to keep track of any clinical sign or symptom of household members during the month following the baseline visit, in a diary, and if so, notify the study team. For symptomatic household participants, study procedures of a possible case report, as detailed above, will be followed. 28 days after symptom onset of the household index case, again a nasal swab and DBS sample will be collected for each household member.

Table 3. Schedule of assessments and samples collected for household transmission investigations.

	Day0 Onset of symptoms of index case	Day X Diagnosis of index case	Day X+1 Sample collection from contacts	Day 28 28 days after onset of index
Index case		nasal swab	DBS	nasal swab + DBS
Household contacts			nasal swab + DBS	nasal swab + DBS

Collected swabs will be stored in viral transport media, kept on conditioned ice packs (0-8°C), then shipped twice a day to a fridge (2-8°C) in the CISPOC office, from where they will be dispatched for PCR-testing at INS in a cooled container (2-8°C) once a day.

Results of PCR testing will be reported once daily from the lab to the national COVID-19 surveillance (also coordinated by INS) and to the study team, who will within two hours inform the possible case on his/her (confirmed or negative) SARS-CoV-2 PCR result by phone and, if an infection is confirmed, provide instructions how to protect household members and when to seek specialized COVID-19 care at the Polana Caniço hospital (according to national guidance).

Confirmed cases will be followed up by phone 28 days and 56 days after symptom onset, to record clinical outcome, using the 'Confirmed case follow-up form'. If not possible to connect by phone, this will be filled in during the subsequent household visit, or through follow-up with the COVID-19 clinical management centre at Polana Caniço General Hospital (if the patient died or is still hospitalised).

The repeated sero-survey, collecting dried blood spots through a finger prick, will be added to the biweekly household visits at 3, 6 and 12 months after COVID-19 local transmission is confirmed. During four other biweekly household visits, the participants selected for the sero-survey will also be interviewed on contact and mobility patterns during the previous day, and uptake of COVID-19 control measures, using the 'Social mixing questionnaire'. Its timing will depend on the stage of the outbreak:

1. shortly after the baseline interview (second visit),
2. when local transmission is well established and the number of new cases is increasing,
3. a month after an initial peak, when the number of new cases is decreasing,
4. during the final study visit.

Table 4 . Forms completed during each study activity

Planned activities	Sample size	Research form
Baseline household visit	15393 individuals (2108 households)	
 
· Informed consent form for population-based COVID-19 surveillance (with household head)
 
· Informed consent form for serial sero-survey (with selected individual)
 
· Baseline household visit form
 

Active syndromic population surveillance	15393 individuals (2108 households) visited every 2 weeks	
 
· Household follow-up visit form
 

Swabbing & PCR testing of symptomatic individuals	possible cases from the surveillance population; initially pooled testing of possible cases; when >50 confirmed cases per week, switch to PCR testing of 1 in 10 suspected cases	
 
· Possible case report form
 
· Possible case lab request and result form
 

Follow-up of PCR confirmed cases at day 28 and day 56 past symptom onset	PCR confirmed cases from the surveillance population	
 
· Confirmed case follow-up form
 

Age-stratified sero-survey at 0, 3, 6, 12 months	2400 individuals/serum samples per round (800 per age group <18yo, 18-50 yo, >50yo NOTE: this is budget dependent, pending cost of	
 
· Sero-survey form
 
· Sero-survey lab request and result form
 

	assay, might be decreased to 1600, spread over two age strata)	
Social mixing survey	the same 2400 individuals selected for the sero-survey; during different HH visits than sero-survey visits	· Social mixing questionnaire
Household transmission investigation	100 household primary cases and their household members (who have been in contact with the index case	· baseline household transmission form

Table 5 . Samples collected during each surveillance and sero-survey study visit

Study visit	Baseline (M0)	Biweekly visit	M3	Biweekly visit	M6	Biweekly visit	M9	Biweekly visit	M12	possible case visit	case follow-up visit (D28)	case follow-up visit (D56)
Tests to carry out	NASAL SWAB											
RT-PCR to detect SARS-CoV-2 viral RNA	*	*	*	*	*	*	*	*	*	*	X	
DRIED BLOOD SPOT (DBS)												
Luminex (anti-SARS-CoV-2 serology)	X		X		X					X		
Approx. volume of collected blood	450ul		450ul		450ul					450ul		

\* A nasal swab will only be collected if an individual is identified as a possible COVID19 case (respiratory symptoms, loss of smell or taste, with or without fever). All tests will be carried out at the INS-Marracuene lab in Maputo, Mozambique.

